### 5.11 Quantitative phase outputs

The output from the quantitative phase will be summary of the women who participated in the quantitative phase, their experience and opinions about pessary self-management and the results of the FGSIS. The findings will also inform sampling for the qualitative phase, as the chief investigator will ensure a stratified sample based upon characteristics, opinions and experience of pessary self-management as well as the FGSIS score. This will ensure the sample in the qualitative phase will be

representative and provide rich data. Collecting quantitative data from women who are not willing to be interviewed about their beliefs ensures these women have the opportunity to express their thoughts and opinions about pessary self-management.

## **6. QUALITATIVE PHASE STUDY DESIGN**

### 6.1 Qualitative phase setting

Women will be recruited from the pessary clinic at Manchester University NHS Foundation Trust and interviewed in person either at the hospital or an alternative venue if preferred, or via video consultation using the 'Attend anywhere' secure technology utilised at Manchester University NHS Foundation Trust for clinical appointments.

### 6.2 Qualitative phase inclusion criteria

- Willing and able to give informed consent
- Female
- Over the age of 18 years
- Have retained a pessary for pelvic organ prolapse for a minimum of two weeks
- Able to speak and understand English or, for those whose first or preferred language is a language other than English, speak a language with an available interpreter

### 6.3 Qualitative phase exclusion criteria

- Lacking capacity to give informed consent
- Has a first or preferred language that is not English, or a language without an available interpreter

The criterion sample of women will be pessary using women who receive pessary care at the women's outpatient department at Manchester University NHS Foundation Trust. In order to ensure a rigorous approach to sampling, criterion sampling will be used whereby all women will have a shared experience of the phenomena of using a pessary (Gray and Grove, 2021). However, to ensure

What affects willingness to self-manage a pessary? - Protocol Version 1.10 04.08.22

a stratified sample, women who have certain characteristics of interest identified during the quantitative phase (for example age, high or low FGSIS scores) and indicated a willingness to receive information about the qualitative interviews will be sent information about the qualitative phase to consider.

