A feminist approach to phenomenological research has previously been utilised to provide detailed description of uniquely female experiences (Zeiler and Käll Folkmarson, 2014). A feminist approach to phenomenological research ensures a focus on women's' perceptions and experiences of sexuality, power relations, privilege, social norms, cultural practices, bodies and desires in a society shaped by men (Zeiler and Käll Folkmarson, 2014). POP, pessary management and self-management of a pessary for POP are uniquely female experiences.

Embodied inquiry is a research approach which promotes the use of different and creative methods to gain greater insight into embodied, lived experience (Leigh and Brown, 2021). Embodied inquiry is suitable where the human body is central and integral to the research question, or where verbal communication may be insufficient to fully explore an issue (Leigh and Brown, 2021). An embodied inquiry approach facilitates the gathering of data which cannot be expressed using words using art-based, dramatic or physical methods (Leigh and Brown, 2021).

Therefore, a feminist phenomenological methodology with an embodied inquiry approach will consider sociological, cultural and historical influences upon women and how this influences willingness to self-manage a pessary. Feminist phenomenology will be used to ensure qualitative data collected provides in-depth understanding of the lived experience of women and how this may affect their willingness to self-manage a pessary.

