### 5.2 Quantitative phase inclusion criteria

- Willing and able to give implied consent by completion of the questionnaire
- Female
- Over the age of 18 years
- Have retained a pessary for pelvic organ prolapse for a minimum of two weeks
- Able to speak and understand English
- Use a ring, shaatz, cube or inflatable pessary

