#### 6.4 Qualitative phase participant identification

The study will be introduced to women receiving pessary management for a prolapse in the women's outpatient department at Manchester University NHS Foundation Trust. If identified while attending the hospital, a clinician will approach the woman and give them an information pack. The CI will also identify women for study participation by screening MFT pessary clinic lists or who have expressed willingness to receive information about the qualitative phase when participating in the quantitative phase. In this instance the study information pack will be posted out to these women by the chief investigator. Following receipt of the information, the woman will be asked to confirm willingness to be interviewed by the investigator by completing and returning an expression of interest form. The investigator will then arrange an appointment for the woman at a convenient time. For women who require a language interpreter, the interview will need to be conducted at MFT to ensure access to the hospital interpretation service, or via video consultation.

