#### 6.9 Qualitative phase sample size

Phenomenological research typically requires a sample size of less than ten prior to data saturation (Moser and Korstjens, 2018). Therefore, a provisional sample size of 10-15 women has been established with awareness that this may be reduced or increased depending upon informational redundancy. Consensus will be sought from the supervisory team and pessary user members of the project management group to ensure all agree saturation of data has occurred and that the themes identified accurately reflect the lived experience of pessary users.

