#### **15. EQUALITY AND DIVERSITY STATEMENT**

All individuals will be considered for inclusion in this study regardless of age, disability, gender reassignment, marriage and civil partnership, pregnancy and maternity, race, religion and belief, sex, and sexual orientation except where the study inclusion and exclusion criteria explicitly state otherwise.

What affects willingness to self-manage a pessary? - Protocol Version 1.10 04.08.22

---

IRAS 304120

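### Interview exclusion 6.3, as written, bars every woman whose first or preferred language is not English, which contradicts the interpreter route in 6.2 and 6.4

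*Combined protocol and SAP*

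**What the plan says.** All references are to the combined protocol and SAP.

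- **Section 6.2 (interview inclusion)** admits women who speak and understand English or, "for those whose first or preferred language is a language other than English, speak a language with an available interpreter".
- **Section 6.3 (interview exclusion)** removes a woman who "Has a first or preferred language that is not English, or a language without an available interpreter".
- **Section 6.4** plans for interpreted interviews: "For women who require a language interpreter, the interview will need to be conducted at MFT to ensure access to the hospital interpretation service", with video consultation as the alternative. It also says how women are found. In clinic, "a clinician will approach the woman and give them an information pack"; the chief investigator also screens clinic lists and contacts survey respondents who agreed to receive information.
- **Section 6.9** sets the size of the phase: "a provisional sample size of 10-15 women has been established".
- **The other phases** have no interpreter route. The survey (5.2) requires "Able to speak and understand English", and 7.2 (development group) and 8.2 (pilot) set the same requirement.
- **Section 5.3 (survey exclusion)** uses the opening words of 6.3 as a complete exclusion in their own right.
- **Section 15** considers all individuals for inclusion "except where the study inclusion and exclusion criteria explicitly state otherwise".

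**The concern.** The interpreter limb of 6.2 and the first limb of 6.3 are triggered by the same characteristic: a first or preferred language other than English. One uses it to admit, the other to exclude. A woman who meets any exclusion criterion is ineligible, so the exclusion prevails and the interpreter limb admits nobody.

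What is at stake is who can be interviewed. The interviews are the only participant phase meant to reach women without English. Section 4.1.2 says the methodology "will consider sociological, cultural and historical influences upon women and how this influences willingness to self-manage a pessary", and section 4.2 takes the interview data forward into the design of the intervention. Losing these women would narrow the range of experience behind both.

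**Working it through.** No sample-size or power figure is involved. The check sets 6.2 against 6.3 for each kind of woman.

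**Notation.** E: she speaks and understands English. I: an interpreter is available for her language. I assume that 6.2 and 6.3 refer to the same language. Women whose first and preferred language is English raise no conflict: 6.2 admits them and 6.3 does not exclude them. The table covers the others.

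**Readings of 6.2.**
- *Either route*: admitted if E or I.
- *Two rules*: English is the test for English-first women, an available interpreter the test for the others. Admitted if I.

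**Readings of 6.3.**
- *Literal*: either limb excludes, so every woman in the table is out.
- *Negation over both limbs*: excludes a woman whose language is neither English nor one lacking an interpreter. That excludes exactly those with I.
- *Charitable*: excludes only if no interpreter is available (not I).

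| Group (first or preferred language not English) | 6.2 either route | 6.2 two rules | 6.3 literal | 6.3 negation over both | 6.3 charitable | Reworded 6.3 |
|---|---|---|---|---|---|---|
| E, I | admits | admits | excludes | excludes | – | – |
| E, no I | admits | does not admit | excludes | – | excludes | – |
| no E, I | admits | admits | excludes | excludes | – | – |
| no E, no I | does not admit | does not admit | excludes | – | excludes | excludes |

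**Groups that 6.2 admits and 6.3 excludes:**

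| Reading of 6.3 | 6.2 either route | 6.2 two rules |
|---|---|---|
| Literal | 3 | 2 |
| Negation over both | 2 | 2 |
| Charitable | 1 (E, no I) | 0 |
| Reworded | 0 | 0 |

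Both grammatical readings of 6.3 contradict 6.2, however 6.2 is parsed. Only a reading that departs from the words restores the interpreter route. Even then, a woman with English whose own language has no interpreter is admitted by 6.2 and excluded by 6.3 on the either-route reading.

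**Does another section cure it?** Section 6.4 shows the intent but sets no eligibility rule. Section 15 defers to the criteria, so it cannot override them. I found no other text that qualifies 6.3.

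**Phases open to women without English.** Survey (5.2) no; interviews (6.2) yes; development group (7.2) no; pilot (8.2) no. That is 1 of 4, or 0 of 4 under a literal 6.3. The clinic observations in 7.10 carry no language criterion, but they are not a listed participant group.

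**The case against.** The best answer is that this is an editorial matter. The intended rule can be recovered from the adjacent criterion and from 6.4. The chief investigator screens lists, takes consent and conducts the interviews, and is unlikely to apply 6.3 against the study's own plan. No section says that the clinicians who hand out packs screen on language. No estimate, sample size or analysis depends on the wording. All of this stands, and it limits the weight of the point.

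Second, 5.3 already keeps women whose first or preferred language is not English out of the survey, so those sampled through the survey have passed the same filter. That also stands: a literal 6.3 adds a restriction only for women reached by clinician approach or list screening. But those are the only ways such women can reach an interview, so the effect falls on exactly the group at issue. Section 5.3 also makes the literal reading a natural one, since the same words are meant literally there.

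Third, rewording 6.3 may not be enough in practice. Section 6.5 requires an information sheet to be read, and 6.8 verbatim transcription, while 6.4 deals only with where or how the interview is held. Any translation needs, however, arise from admitting these women under 6.2 and 6.4, not from correcting 6.3. The supporting documents were not available, so I do not say that translated materials are missing.

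Fourth, language is not culture, and ethnicity is recorded separately. That is fair: the link to 4.1.2 is a plausible consequence, not a demonstrated one.

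**Conclusion.** The concern holds. Section 6.3 is wrong as written and should be corrected. It is an operative eligibility rule that, followed to the letter, shuts out the women for whom 6.2 and 6.4 make provision.

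Its reach is the 10-15 interviews and, among them, women approached in clinic or found on clinic lists. How many would be lost cannot be stated without the clinic's language mix. The survey target of 90 is unaffected. The contradiction rests on the wording alone. The view that it is a slip, and that literal application is unlikely, is inferred from 6.2, 6.4 and the chief investigator's role.

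**What to change.** Replace the language exclusion in 6.3 with a single joint condition, for example: *Neither speaks and understands English nor speaks a language for which an interpreter is available.* This excludes no woman whom 6.2 admits, on either reading of 6.2.

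It would be tidy to settle 6.2 in the same amendment by stating whether a woman who speaks English, but whose first or preferred language has no interpreter, is eligible. On the two-rule reading she would still fail 6.2, although the new 6.3 would not exclude her.

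The cost is one criterion reworded (plus a clarifying clause in 6.2 if wanted), handled under section 12.2. Interpreter use is already planned in 6.4, and sample size and analysis do not change.

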#### 6.4 Qualitative phase participant identification

The study will be introduced to women receiving pessary management for a prolapse in the women's outpatient department at Manchester University NHS Foundation Trust. If identified while attending the hospital, a clinician will approach the woman and give them an information pack. The CI will also identify women for study participation by screening MFT pessary clinic lists or who have expressed willingness to receive information about the qualitative phase when participating in the quantitative phase. In this instance the study information pack will be posted out to these women by the chief investigator. Following receipt of the information, the woman will be asked to confirm willingness to be interviewed by the investigator by completing and returning an expression of interest form. The investigator will then arrange an appointment for the woman at a convenient time. For women who require a language interpreter, the interview will need to be conducted at MFT to ensure access to the hospital interpretation service, or via video consultation.

#### 6.5 Qualitative phase consent

For the qualitative phase, informed consent will be obtained by the chief investigator. The chief investigator will have completed recent Good Clinical Practice training as per the Sponsor's requirements. During the informed consent process, a discussion will take place between the potential participant and the chief investigator about the research, the nature and objectives of the study and possible risks associated with their participation. Potential participants will also be given the opportunity to ask any questions they have. A participant information sheet reviewed by the Sponsor, REC and HRA will be given and read by all participants before written informed consent is obtained. Capacity to give informed consent will be assessed by a member of the research team in accordance with training to assess capacity provided by the sponsor. For women who choose to have

a face to face interview, informed consent will be obtained via a paper consent form. For women who prefer to have their interview conducted remotely via 'attend anywhere', the informed consent process and verbal consent will be video recorded following permission from the woman prior to the call. The consent to record will be confirmed before and after pressing Record. The video recording will be stored securely on the chief investigator's password protected account on the MFT NHS hospital server. The chief investigator will obtain recorded verbal agreement to each point on the consent form. Remote participation in the interview also acts as confirmation that the participant is willing to continue in this way. Following the informed consent process, the video recording will be stopped and the audio recording commenced. The video recording of confirmation will be emailed securely to each participant. If the recording is lost or fails, the woman will be contacted again and asked to sign a paper consent form either in person (if preferred), or via post, in which case a consent form will be posted to her with a stamped, addressed envelope. If returned via post, the consent form will be signed by the researcher upon receiving the consent form signed by the woman. The consent date for the researcher will be the date the form is received in the post. The consent process, whether face to face or during video consultation as well as any need to re-consent will be documented in the woman's hospital records.

#### 6.6 Qualitative phase payment/reimbursement

- £10 shopping voucher following interview
- £10 shopping voucher upon receipt of a photograph or presentation of participant's identity box

Maximum total £20

#### 6.7 Baseline data

Descriptive data about the women who are participating in the research will be collected by the researcher from the woman or medical records if necessary (for example if a woman isn't sure of the type or size of her pessary) and recorded on a paper case report form). Should the woman have

previously completed a questionnaire in the quantitative phase, this data will be verified with the woman, but will not need to be collected again if still correct.

- Year of birth
- Length of time pessary used for
- Type and size of pessary in situ
- Comorbidities
- Self-management status
- Self-management experience
- Self-management willingness
- Ethnicity
- Post code
- Level of education
- Female Genital Self-Image Score (FGSIS)

#### 6.8 Qualitative phase data collection

Data collection will be via semi-structured interviews. An interview guide will be used to structure the interviews. This guide has been developed based upon findings of a scoping review and systematic review undertaken by the chief investigator in addition to wider reading of similar studies exploring the lived experience of being a woman from a feminist perspective. The interviews will be conducted by the chief investigator either in person or via video consultation depending upon the participants' preference. The interviews will be audio recorded, anonymised and transferred to a professional transcription service by their encrypted file transfer page. Upon receipt by the professional transcription service, the audio recording will be transcribed verbatim then returned to the researcher for coding. The chief investigator will also make field notes recording observations, emerging themes and concepts, methodological issues and a summary of the data collected and how this contributes towards research findings (Groenewald, 2004).

An embodied enquiry approach will also be utilised whereby data will also be gathered by asking participants to collect an identity box prior to the interview which reflects their physical, psychological and emotional experiences of having prolapse, using a pessary or self-management of a pessary. Women will be asked not to include any items which would identify themselves or anyone else for, example by including personal photos or using names. The women will be asked to take a photograph of the identity box or bring the identity box to the interview if preferable and convenient in which case the researcher will take a photograph of the identity box. The researcher will engage the woman in discussion about the contents of their identity box to ensure understanding of how the items reflect their lived experience. Photographs of the identity boxes will be used in the dissemination of findings to further illustrate women's physical, psychological and emotional experiences which cannot be explained using spoken word.

#### 6.9 Qualitative phase sample size

Phenomenological research typically requires a sample size of less than ten prior to data saturation (Moser and Korstjens, 2018). Therefore, a provisional sample size of 10-15 women has been established with awareness that this may be reduced or increased depending upon informational redundancy. Consensus will be sought from the supervisory team and pessary user members of the project management group to ensure all agree saturation of data has occurred and that the themes identified accurately reflect the lived experience of pessary users.

#### 6.10 Qualitative phase data analysis

The process of making field notes represents the commencement of data analysis, as reflecting upon the data collected, the meaning derived from this, how it directs future data collection and fits with previous data collected is analysis (Groenewald, 2004). Formal analysis of the collected data will be undertaken using an interpretive phenomenological approach described by Smith and Shinebourne (2012). The first step is becoming immersed in the interview transcript to ensure familiarity with the findings, making notes and annotations as required (Smith and Shinebourne, 2012). After this, the transcript will be re-read and emerging themes noted (Smith and Shinebourne, 2012). The next stage

is to look for connections between the themes identified within the transcript and create clusters while constantly referring to the original transcript to verify interpretations being made (Smith and Shinebourne, 2012). The final stage of transcript analysis is to create a table of themes, structured to prioritise themes rich in evidence and which accurately reflect the interview (Smith and Shinebourne, 2012). Clusters will be renamed to reflect the superordinate and subordinate themes recorded within them (Smith and Shinebourne, 2012). The step by step process will be utilised for the analysis of further transcripts, however the researcher will use the analysis of prior transcripts to examine whether there are similarities and differences in the data gathered from women (Smith and Shinebourne, 2012). Once each transcript has been analysed, a master table of superordinate and subordinate themes identified within the whole data set will be created (Smith and Shinebourne, 2012). Smith and Shinebourne (2012) clarify that themes should be included and prioritised within the table based upon the richness of data supporting the theme and how accurately it reflects the accounts given by participants rather than the frequency of which they are identified. In accordance with the feminist approach the chief investigator will consider whether the themes identified represent gender differences or power imbalances acknowledging the structural implications of society, culture and politics for being a woman (Clifford et al., 2019).

